7.1 Study Subjects

7.1.1 Disposition of Subjects

Subject disposition (e.g., number completing the study, number lost-to-follow-up) will be summarized with frequency tables.

7.1.2 Clinical Investigation Plan (CIP) Deviations

CIP deviation is defined as an event where the Investigator or study personnel did not conduct the study according to the CIP. Deviations shall be reported regardless of whether medically justifiable or taken to protect the subject in an emergency.

7.1.3 Analysis Sets

The following population will be considered the primary population, but not limited to, in the analysis of data for this study: Intent to Treat Population.

The Intent to Treat (ITT) population includes all subjects who have signed and dated the patient informed consent (ICF) or Data Release Form (DRF) and in whom deployment of the Pipeline™ Flex Embolization Device with Shield Technology™ was attempted.

7.2 General Methodology

All statistical analyses will be performed using Statistical Analysis System (SAS) for Windows (version 9.2 or higher, SAS Institute Inc. Cary, NC) or other widely accepted statistical or graphical software. In general, data for all study Subjects combined will be presented. Individual data will be presented in subject listings.

Descriptive statistics will be used to present the data and to summarize the results. Discrete variables will be presented using frequency distributions and cross tabulations. Continuous variables will be summarized by presenting the number of observations (N), mean, standard deviation, median, minimum, and maximum values.

For Adverse Event reporting, which includes primary and secondary variables, the primary analysis will be based on Subject counts (e.g., the number and percentage of Subjects with event among the total number of Subjects). The data will be presented in the format of p% (x/N) [e], with p and x being the percentage and number of Subjects with events, respectively, N being the sample size of the analysis population, and e being the total number of events occurred in the x Subjects.

For device-related outcomes (e.g., device deployment success rate), the unit of analysis will be the device.

For occlusion outcomes, the unit of analysis will be the aneurysm.

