1.2.3 Clinical Study Experience

The clinical benefits achieved with the use of use of Pipeline™ Embolization Device have been consistently demonstrated in multiple clinical trials.²⁶⁻³⁶ Pipeline™ Embolization Device demonstrates high efficacy and a good safety profile in treating aneurysms of diverse morphology, ranging from small to more complex and difficult to treat aneurysms (e.g. large aneurysms, wide-

neck aneurysms, or aneurysms with complex morphology).^{27,30,37,39-41} Clinical outcomes from 5 key studies sponsored by Medtronic/Covidien have been summarized below:

Pipeline for Intracranial treatment of Aneurysms (PITA)

The PITA study was the first prospective multicenter trial of a flow-diverting construct for the treatment of complex large and giant IAs.²⁷ Thirty-one subjects with wide-necked (>4 mm) and unfavorable dome/neck ratios (<1.5 mm) and subjects with an IA that had failed previous endovascular treatment were included. Of the 31 aneurysms, 65% were small (<10 mm) and the remaining 35% were large and giant in size. In total, 46 of 47 Pipeline™ device braids were placed successfully (97.9%). In 30 out of 31 subjects, the entire neck of the targeted intracranial aneurysm was covered by the Pipeline™ device braid. Complete aneurysm occlusion was observed in 93.3% (28/30) subjects at 180 days. Two subjects experienced a major periprocedural stroke and no deaths occurred.

Pipeline™ Embolization Device for Uncoilable or Failed Aneurysms (PUFs)

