4.3 Study Population

The study population will consist of subjects who have an intracranial aneurysm and are enrolled in the study. The treated aneurysm may be ruptured (with a Hunt and Hess grade of ≤ 3) provided that the Pipeline™ Flex Embolization Device with Shield Technology™ is used according to its Instructions for Use and its intended use during the treatment regimen.

For subjects with more than one aneurysm requiring treatment, the following guidance is to be followed for subjects to be enrolled in the study.

- If more than one aneurysm can be covered by a single Pipeline device or two overlapped devices, the multiple aneurysms treated by that device(s) may all be included in the study. A maximum of two overlapped devices in consecutive arterial segments will be permitted. The largest aneurysm meeting criteria will be designated the target aneurysm. For equal sized aneurysms, the Core Lab will designate the target aneurysm.
- If the subject has more than one aneurysm and all aneurysms requiring treatment cannot be covered by a single Pipeline device or two overlapped devices, the non-target aneurysms should be treated first. After waiting at least 30 days per exclusion criterion #1 below, the subject may return for Pipeline treatment of the target aneurysm.

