9 STATISTICAL METHODS AND DATA ANALYSIS

9.1 General Principles

Descriptive statistics will be used to present the data and to summarize the results. For continuous variables, statistics will include means, standard deviations, medians and ranges, as appropriate. Categorical variables will be summarized in frequency distributions. In general, data for all study subjects combined will be presented. Individual data will be presented in subject

listings. Statistical analyses will be conducted in SAS version 9.1 or above (SAS Institute, Cary, NC) or other validated statistical software package.

For adverse event reporting, the primary analysis will be based on subject counts (e.g., the number and percentage of subjects with event among the total number of subjects). The data will be presented in the format of p% (x/N) [e], with p and x being the percentage and number of subjects with events, respectively, N being the sample size of the analysis population, and e being the total number of events occurred in the x subjects.

For device-related outcomes (e.g., device deployment success rate), the unit of analysis will be device.

For occlusion outcomes, the unit of analysis will be the aneurysm.

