Subjects will be considered enrolled in the study once the patient has signed and dated the Informed Consent or DRF and the Pipeline™ Flex Embolization Device with Shield Technology™ is advanced into the micro catheter inside the patient. All enrolled subjects who underwent the study procedure and in whom an attempt to implant the device was made will be included in the analysis population.

A CEC will be in place for the study using a minimum of three physicians knowledgeable in the appropriate disciplines and medical specialties pertinent to the disease state being evaluated in this clinical study. This committee will be responsible for the review and adjudication to the study variables of all events identified in the CEC Charter/Manual of Operations.

The CEC will independently adjudicate to specified endpoint event definitions, event relatedness, event severity, and event outcomes.

The imaging core laboratory will be responsible for the qualitative image analysis to determine aneurysm occlusion, parent artery stenosis, and device migration. An imaging protocol will be provided to the site.

Pre-Specified Study Endpoints:

The pre-specified study endpoints and analysis listed here are the primary body of data that will be collected, analyzed, and summarized in a series of tables, lists, and graphs as part of the final report for this study. Other analysis will be conducted as part of the final report but these are the core set of analyses that will constitute the foundation of the clinical study report.

Primary endpoints:

Safety:

- Occurrence of major stroke in the territory supplied by the treated artery or neurological death post-procedure (1-year)

Effectiveness:

- Complete aneurysm occlusion (defined as Raymond-Roy grade 1) without significant parent artery stenosis ($\leq 50\%$) or retreatment of the target aneurysm post-procedure (1-year)

Secondary endpoints:

Safety:

- Occurrence of major stroke in the territory supplied by the treated artery or neurological death at 30 days post-procedure due to procedural complications
- Delayed intracerebral hemorrhage > 30 days post-procedure

Effectiveness:

- Device deployment success rate at the target site

Additional Safety Analyses:

- [REDACTED]
- [REDACTED]

- [REDACTED]
 - [REDACTED]
 - [REDACTED]

Additional Effectiveness Analyses:

- [REDACTED]
 - [REDACTED]
 - [REDACTED]
- [REDACTED]
- [REDACTED]
- [REDACTED]
- [REDACTED]
- [REDACTED]

Study Procedure:

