The patient will be tested at the discretion of the site per standard of care procedures for antiplatelet response and the appropriate dose of antiplatelet agents will be given after the Pipeline™ device with Shield Technology™ placement procedure. Medications could be continued as medically indicated.

Estimated Duration of Patient Participation

Up to 200 subjects will be enrolled over a period of approximately 24 months. The study is intended to have 200 subjects undergo attempted deployment of the Pipeline™ device with Shield Technology™. Each study patient will be followed for 1 year after the primary study procedure. Study participation includes consent, initial screening and baseline, treatment using the Pipeline™ device with Shield Technology™, discharge exam and follow-up visits at approximately 30, 90, 180 days, and 1 year. The total study duration is expected to be approximately 3 years.

Schedule of Assessments

	Baseline	Procedure	Discharge	1 Month	3 Months	6 Months	1 Year	Unscheduled
Schedule		Day 0		±14 days	±30 days	±6 weeks	±8 weeks	
Eligibility	X							
Demographics	X							
Aneurysm Symptoms	X	O	O	O	O	O	O	OR
Medical History		X						
Study Procedure		X						
Procedure Imaging		XR						
Ancillary Devices		X						
Study Device		XR						
Discharge			X					
Follow Up				X	X	X	X	XR
Follow-Up Imaging				OR	OR	OR	OR	OR
NIHSS	O	X		O	O	O	O	OR
mRS	O	X		O	O	O	O	OR
Exit			X					

Retreatment Study Procedure				OR	OR	OR	OR	OR
Labs	OR	OR	O	O	O	O	O	OR
Device Specific Event		OR	OR	OR	OR	OR	OR	OR
Adverse Event Assessment		OR	OR	OR	OR	OR	OR	OR

Key: Required=X Optional=O Repeatable=R

ANALYSIS POPULATIONS

The following populations will be considered for the analysis of data for this study:

Intent to Treat (ITT)

The Intention to Treat (ITT) population includes all consented subjects in whom deployment of the Pipeline™ device with Shield Technology™ was attempted.

Full Analysis Set (FAS)

The Full Analysis Set (FAS) population is a subset of the ITT population including only those subjects in whom the Pipeline™ device with Shield Technology™ was implanted.

Internal Carotid Artery (ICA) Population

The Intra-Cranial Artery Population (ICA) is a subset of the ITT population including only those subjects in whom the Pipeline™ device with Shield Technology™ was implanted in the ICA (segments C2-C7).

Non-ICA Population

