The non-ICA is a subset of the ITT population including only those subjects in whom the Pipeline™ device with Shield Technology™ was implanted in the arterial vessels other than those specified in the ICA population.

6. Determination of Sample Size

No formal estimates were prepared for examining the individual variables. However, the incidence of certain events will be examined relative to the thresholds used in research treating a similar population. Device outcomes variables recorded on a dichotomous scale will be summarized using a 2-sided 95% Clopper-Pearson exact binomial confidence interval. The upper and lower bounds of the confidence interval will be examined relative to results in the peer-reviewed literature and studies using the

Pipeline device without the Shield Technology™. Specifically, the incidence at 1 year post-procedure of a major stroke in the territory supplied by the treated artery or neurological death will be examined relative to an a priori threshold of 15%. The incidence at 1 year post-procedure of aneurysm occlusion without significant parent artery stenosis will be examined relative to an a priori threshold of 50%.

7. Statistical Methods

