- [REDACTED]
- [REDACTED]
- [REDACTED]

[REDACTED]

[REDACTED]

- [REDACTED]
- [REDACTED]

Pipeline™ Device with Shield Technology™ Deployment

A summary of the use of the Pipeline™ devices for the ITT population will be presented in a table entitled *Summary of Pipeline™ Device Deployment*; a similar table will be restricted to the ICA population. The number of Pipeline™ devices used and the reasons for multiple device use for the primary study procedure will be presented. The count and percentage for the following categories applicable to the SHIELD device will be summarized:

[REDACTED]

[REDACTED]

[REDACTED]

[REDACTED]

[REDACTED]

[REDACTED]

- [REDACTED]
- [REDACTED]

[REDACTED]

- [REDACTED]
- [REDACTED]
- [REDACTED]
- [REDACTED]
- [REDACTED]

Side branches covered by PFED?

- [REDACTED]
- [REDACTED]
- [REDACTED]
- [REDACTED]
- [REDACTED]
- [REDACTED]
- [REDACTED]
- [REDACTED]
- [REDACTED]
- [REDACTED]
- [REDACTED]
- [REDACTED]
- [REDACTED]
- [REDACTED]
- [REDACTED]
- [REDACTED]
- [REDACTED]
- [REDACTED]
- [REDACTED]
- [REDACTED]
- [REDACTED]
- [REDACTED]
- [REDACTED]
- [REDACTED]
- [REDACTED]
- [REDACTED]
- [REDACTED]
- [REDACTED]
- [REDACTED]
- [REDACTED]
- [REDACTED]
- [REDACTED]
- [REDACTED]
- [REDACTED]
- [REDACTED]
- [REDACTED]
- [REDACTED]
- [REDACTED]
- [REDACTED]

- [REDACTED]
- [REDACTED]
- [REDACTED]
- [REDACTED]
- [REDACTED]
- [REDACTED]
- [REDACTED]
- [REDACTED]

The supportive data for ancillary devices table will be presented in a listing entitled *Ancillary Devices*. This listing will be sorted by patient number. The list of study devices will be presented in a listing entitled *Pipeline™ device with Shield Technology™ Accountability*.

Overall Summary of Device and Peri-Procedure Variables

The overall summary of the results (site reported when Core Lab adjudicated data not available) from the study procedure will be summarized in a table entitled *Overall Summary of the Device and Peri-Procedure Variables*; a similar table will be restricted to the ICA population. Within this table, 9 separate parameters will be summarized:

- Successful deployment of the study device to the target site. Successful deployment has a binary outcome and comes directly from the clinical case report form.
- Implantation of the study device. The determination of implantation has a binary outcome and comes directly from the clinical case report form.

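### Device deployment success is analysed per device with an exact binomial interval that ignores subjects who receive more than one device, so the interval can be modestly too narrow.

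*SAP*

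**What the plan says.** SAP 5 and SAP 7.9 list one secondary effectiveness endpoint: "Device deployment success rate at the target site". Protocol 9.1 and SAP 7.2 agree on the unit. The SAP's words are: "For device-related outcomes (e.g., device deployment success rate), the unit of analysis will be the device".

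The interval method stands in SAP 6: "Device outcomes variables recorded on a dichotomous scale will be summarized using a 2-sided 95% Clopper-Pearson exact binomial confidence interval". The same section says that the bounds will be examined against the literature and against Pipeline studies without the Shield coating.

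More than one device per subject is foreseen. Protocol 4.3, in its guidance on subjects with more than one aneurysm, says: "A maximum of two overlapped devices in consecutive arterial segments will be permitted". SAP 7.7 plans for it in reporting: "The number of Pipeline™ devices used and the reasons for multiple device use for the primary study procedure will be presented".

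The unredacted text gives no clustered interval, GEE, mixed model, first-device rule or per-subject version of this endpoint. Parts of the deployment section of SAP 7.7 are blacked out, and nothing is inferred from them.

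**The concern.** Clopper-Pearson is exact for independent trials. Two devices placed in one subject at one procedure share vessel anatomy, access and operator, so a difficult case can defeat both. If their outcomes are positively correlated, 303 devices carry less information than 303 independent trials, and the planned interval claims too much precision.

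What is at stake is limited but not nothing. SAP 6 uses the bounds for comparison with earlier Pipeline results, and SAP 3 says that the analyses may support a US indication evaluation. A bound used in that way should have about the coverage it states.

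**Working it through.** **Reference figure.** The plan states no expected rate, interval width or power for this endpoint, so there is no design figure to reproduce. The nearest figure is the PITA result in Protocol 1.2.3: 46/47 = 97.9%, which reproduces. Its plain Clopper-Pearson 95% interval is 88.7% to 99.9%.

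**Inputs.**
- Subjects: 200 with attempted deployment (SAP 5, estimated duration of participation).
- Devices per subject: PITA used 47 devices in 31 subjects, 47/31 = 1.52. Taken here as 103 subjects with two devices and 97 with one: 2 × 103 + 97 = 303 devices. Two devices for every subject (400 devices) is the unfavourable case.
- Assumed, because the documents do not give them: success of 95% (97.9% as a variant) and an intraclass correlation (ICC) from 0 to 1.

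**Design effect.** Because the number of devices varies by subject, the size-weighted form applies:

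DE = 1 + (Σm²/Σm − 1) × ICC

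Σm² = 103 × 4 + 97 × 1 = 509, and 509/303 − 1 = 0.68. So:
- ICC 0.1: DE = 1 + 0.068 = 1.07
- ICC 0.3: DE = 1 + 0.204 = 1.20
- ICC 0.5: DE = 1 + 0.340 = 1.34
- ICC 0.8: DE = 1 + 0.544 = 1.54

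**Interval.** For 288/303 = 95.0%, plain Clopper-Pearson is compared with Clopper-Pearson on the effective sample size, 303/DE:

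| ICC | DE | Effective n | 95% interval |
|---|---|---|---|
| 0 (as planned) | 1.00 | 303 | 92.0% to 97.2% |
| 0.1 | 1.07 | 284 | 91.8% to 97.3% |
| 0.3 | 1.20 | 252 | 91.6% to 97.4% |
| 0.5 | 1.34 | 226 | 91.4% to 97.5% |
| 0.8 | 1.54 | 196 | 91.0% to 97.6% |

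The missing width is a factor of about √DE: 1.03, 1.10, 1.16 and 1.24 for ICC 0.1, 0.3, 0.5 and 0.8.

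**Coverage of the planned interval.** Simulated with 20,000 trials per cell, 200 subjects and exchangeable correlation within subject:

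| ICC | 1.5 devices, 95% success | 1.5 devices, 97.9% success | 2 devices, 95% success |
|---|---|---|---|
| 0 | 96.7% | 97.6% | 96.2% |
| 0.1 | 96.1% | 96.9% | 95.2% |
| 0.3 | 94.8% | 95.9% | 93.3% |
| 0.5 | 93.2% | 94.5% | 90.9% |
| 0.8 | about 91.6% | 93.0% | 87.4% |

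The first column can be checked by enumeration. With p the success rate, a two-device subject has both successes with probability p² + ICC·p(1 − p), both failures with (1 − p)² + ICC·p(1 − p), and one of each otherwise. Convolving 103 such pairs with a binomial for the 97 single devices gives 94.8%, 93.4% and 91.3% at ICC 0.3, 0.5 and 0.8, within 0.3 points of the simulation.

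Coverage of an exact interval is uneven in p. In a separate simulation at 98% rather than 97.9% success it was 94.6%, 93.2% and 90.8% at the same three correlations.

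**The case against.** **The correlation is unquantified.** This stands. The chance that a second device fails given that the first did is q + ICC × (1 − q), with q the failure rate. At 98% success that is 0.02 + 0.5 × 0.98 = 51% at ICC 0.5, and about 80% at ICC 0.8. Nothing in the documents supports or excludes such values. At ICC 0.3 or below with 1.5 devices per subject, coverage is essentially nominal because Clopper-Pearson is conservative.

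**The device count is borrowed.** The ratio of 1.5 comes from one study of 31 subjects with an earlier device. This stands too, and it is why two devices per subject is shown beside it.

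**Replacement after failure is not a cause.** A reader might infer that opening a further device because the first failed makes the interval too narrow or biases the rate. It does not do so by itself. With independent outcomes and a second device only after a failure, simulated coverage was 96.0% at 95% success and 96.1% at 90%, and the mean estimates were 95.0% and 90.0%. Only positive correlation, such as from shared anatomy and operator, produces the loss.

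**Nothing is decided on this interval.** A reader might also infer that a study conclusion is at risk. The documents do not support that. The protocol sets no success criteria (9.2), the 15% and 50% thresholds in SAP 6 belong to the primary endpoints, and primary effectiveness uses one target aneurysm per subject (SAP 7.7). The table that reports deployment in SAP 7.7 names no interval, so the method comes only from the general sentence in SAP 6. That sentence does cover a dichotomous device outcome.

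**Something per subject is already planned.** The SAP counts implant failures per subject and separates attempted from implanted subjects. This helps, but it is not deployment success at the target site and has no stated interval.

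**Conclusion.** The point holds as a minor one. The independence behind the planned interval is not secured by the design, and the plan makes no allowance for that. The interval can be too narrow; the documents do not show that it will be.

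At about 1.5 devices per subject and 95% success, coverage falls to about 94.8%, 93.2% and 91.6% at ICC 0.3, 0.5 and 0.8, with no loss at 0.1. The lower limit moves from 92.0% by 0.4, 0.6 and 1.0 points respectively. If every subject received two devices, the loss would be larger. The size rests on the assumed correlation, success rate and device count. No test or threshold is affected.

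**What to change.** - Keep the per-device success rate as the estimate.
- Take its 95% interval from a method clustered on subject that holds up near 100% success. One choice is a logit-link GEE with robust variance, using an independence working correlation so that the point estimate stays the per-device rate. The alternative is Clopper-Pearson on the effective sample size, devices/DE. At 95% success both kept coverage at about 95% to 97% in simulation.
- If there are no failures, revert to plain Clopper-Pearson and say so in the SAP.
- Do not use a percentile bootstrap or an identity-link GEE. At 98% success, in simulation, the bootstrap covered 89.0% to 92.5% and the identity-link GEE 89.1% to 93.7% over ICC 0.1 to 0.8, both below the planned interval. With no failures the bootstrap interval collapses to a point.
- Report beside it the per-subject deployment success rate with a Clopper-Pearson interval, and define in advance what counts as success when a subject has more than one device. With one outcome per subject, within-subject clustering does not arise.

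The cost is a few sentences in SAP 6 and 7.2, minor programming and a slightly wider interval. No new data are needed.

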7.2.1 Analysis Conventions

Specific algorithms are discussed for imputing missing or partially missing dates, if deemed appropriate, under specific data topics. Imputed or derived data will be flagged in the individual patient data listings. Imputed data will not be incorporated into any raw or primary datasets. These data are retained in derived (or analysis) datasets.

The term *Primary Study Procedure* refers to the initial study procedure, *Re-treatment Procedure* refers to the treatment performed after the *Primary Study Procedure*.

Total duration on study will be calculated as the difference between the date of procedure (Day 0) and the last on-study observation. All calculations defining the duration on study will be performed relative to the date of procedure and follow the algorithm $DURATION = [STUDY\ COMPLETION\ OR\ WITHDRAW\ DATE - PROCEDURE\ DATE]$.

Post-procedure angiograms will be reviewed to assess aneurysm occlusion according to the scale of Roy:

- Complete = Complete occlusion, no flow of contrast seen in the aneurysm sac
- Residual Neck = Partial occlusion, some flow or eddying flow in the aneurysm sac
- Residual Aneurysm = Incomplete occlusion, apparent flow in the aneurysm sac

Procedure time will be calculated based on the following sentinel events. Start Time: Time of skin incision. End Time: skin closure

Major Stroke: A stroke, in which the NIHSS of the subject increases by ≥ 4 and persists for 7 days and more.

Minor Stroke: A stroke, which resolves completely within seven days OR increases the NIHSS of the subject by ≤ 3 .

Neurological Death is any patient death due to neurological reasons.

